9. RESEARCH METHODS

9.1. Study Design

A retrospective comparative cohort design will serve as the primary study design. It will compare the incidence rate of outcomes of interest among those who received ABRYSVO to the incidence rate in a random sample of unvaccinated older adults from the same underlying population of interest (i.e, immunocompromised, renally impaired, or hepatically impaired, evaluated as separate populations and if appropriate, as a combined population). The index date for the vaccinated individuals will be defined as the date of administration of ABRYSVO. The unvaccinated cohort will be assigned an index date matched to a corresponding index date in the vaccinated cohort based on calendar time. Due to potential limitations in sample size, matching on additional variables will not be conducted. Instead, (PS) methods incorporating a greater number of covariates will be considered to create weight-adjusted vaccinated/unvaccinated cohorts.

[figure not shown]
PFIZER CONFIDENTIAL

In addition to the primary study design (i.e, comparative cohort design), for an appropriate subset of the study outcomes (see Table 1), the SCRI design will also be used. Among individuals vaccinated with ABRYSVO and experiencing a subset of outcomes, the incidence during a post-vaccination risk interval will be compared to the incidence in a post-vaccination control interval. The within-person SCRI design considers only vaccinated individuals with the specific outcome of interest and inherently controls for time-invariant confounders (such as sex, race, chronic illness, and health state). The risk and control intervals are based on a review of the published literature and precedence from previous studies of vaccine safety (see Table 1).

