9.3. Variables

9.3.1. Exposure Definition

Exposure will be based on recorded prescription, dispensing, or administration of ABRYSVO. Vaccine receipt and date of vaccination will be obtained from all available sources that capture ABRYSVO vaccination, such as pharmacy dispensing records, general practice records, immunization registers, vaccination records, medical records, or other secondary data sources. Depending on the data source, vaccines will be identified via

PFIZER CONFIDENTIAL CT24-WI-GL02-RF02 5.0 Non-Interventional Study Protocol Template For Secondary Data Collection Study 01-Aug-2023

Page 28 of 72

nationally used product codes where possible. The main exposure of interest is in the receipt of ABRYSVO.

- **CPRD Aurum (UK):** Data on vaccine exposure will be identified using CPRD Product Codes (PRODCODE ID's) and/or Medical Codes (MEDCODE ID's) based on available codes in CPRD product and medical dictionaries. Vaccination data originate from the patient primary care electronic medical records held within CPRD. The information captured at the individual patient level includes the name of the vaccine; manufacturing company; dose; stage of the vaccine schedule (if applicable); administration route; administration location (e.g., general practice); date of administration; and medical observations, events, referrals, test results, and prescribed medications recorded by the GP prior to, on, or after the vaccination date.
- VID (ES): Data on vaccine exposure are obtained from patient level electronic records within the vaccine information system which captures information on vaccine type, manufacturer, number of doses, location and administration date, adverse reactions related to vaccines, and if applicable, risk groups. Vaccines information in the VID is updated daily.
- **SIDIAP (ES):** Data are available on all routine childhood and adult immunizations, including the antigen and the number of administered doses. Vaccination information originates from patient electronic medical records. For each patient, SIDIAP has the date and centre of administration, dose, brand, reasons for vaccination (e.g., risk of group), and other information related to vaccination.
- **EpiChron (ES):** The EpiChron cohort provides data of individuals' pharmacotherapeutic history, including vaccination, with prescriptions and dispensation of drugs in community pharmacies, coded according to the WHO ATC classification system.

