- **SNDS (FR):** Exposure information is captured based on vaccines dispensed in community outpatient pharmacies. Exposure information will be coded using the ATC classification system as well as a specific French pharmacy codes (CIP) and European Pharmaceutical Market Research Association codes, with dates of prescription and dispensing.

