a. Day 0 is the date of vaccine administration (i.e, index date for the vaccinated cohort in the comparative cohort design and SCRI design) or matched index date (for the unvaccinated cohort in the comparative cohort design) b. To align with ongoing postmarketing study C3671031, A Post-Authorization Safety Study of Guillain-Barré Syndrome (GBS) Following ABRYSVOTM Among Older Adults in the United States, sensitivity analyses will be performed for GBS, acute disseminated encephalomyelitis, and transverse myelitis using shorter risk intervals of 1-21 days, 5-28 days, and 1-21 days, respectively. Further details are outlined in Section 9.7.4. c. Published risk and control intervals for demyelinating diseases and cranial disorders were applied to transverse myelitis and narcolepsy/cataplexy.

d. Please note that alternative risk windows were reported in other studies.

e. To align with ongoing postmarketing study C3671037, A Post-Authorization Safety Study of Atrial Fibrillation Following Respiratory Syncytial Virus Vaccine (ABRYSVOTM) Among Older Adults in the

PFIZER CONFIDENTIAL

CT24-WI-GL02-RF02 5.0 Non-Interventional Study Protocol Template For Secondary Data Collection Study 01-Aug-2023

Page 31 of 72

Table 1	List of Select Adverse Events of Special Interest
---------	---

Body system/	Adverse event of special interest	Estimated risk	Analytic Approach
classification		window (days) ^a .	

Veterans Affairs Health System, sensitivity analysis will be performed for atrial fibrillation and supraventricular arrhythmias using a shorter risk interval of 0-3 days. Alternative risk intervals of 0-1 day or 0-30 days may also be considered. Details are provided in Section 9.7.4.

f. Similar risk and control intervals were applied to all cardiovascular and haematological disorders characterised by damage to the blood vessels and/or arteries and clotting (i.e, coagulation disorders and single organ cutaneous vasculitis).

g. Risk intervals for most outcomes start on Day 1 post-index, but for some outcomes, the risk interval starts on the day of vaccination due to biological plausibility of rapid onset following vaccination.

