- Medication dispensed in community outpatient pharmacies recorded as dispensed preparation packs, with dates (prescription and dispensing): drug information includes ATC code, CIP code (French pharmacy coding system), and EPhMRA code; description of packs in number of tablets and strength; the number of packs dispensed; date of prescription and nature of prescriber, date of dispensing, and the dispensing pharmacy (anonymised). Information on underlying medical indication or date of drug injection are not available. Vaccinations are captured within this data file.

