CT24-WI-GL02-RF02 5.0 Non-Interventional Study Protocol Template For Secondary Data Collection Study 01-Aug-2023 Page 53 of 72 comparative cohort design. Use of the complementary SCRI design, where appropriate, is therefore a strength as this relies upon individuals for which there is a record of vaccination and is not subject to potential misclassification of vaccination status. It is also possible that some outcomes are the result of immunization errors occurring during the administration of ABRYSVO. This information is not collected regularly and will not be accounted for with the current protocol.

Similarly, outcomes are based on coded events captured in the databases and misclassification due to coding errors, or use of sub-optimal algorithms, may lead to misclassification bias. The databases proposed for this study all have access to linked primary and secondary care data to maximize capture of outcomes of interest. In addition, this study proposes to use outcome algorithms from the ACCESS project which have now been widely applied in vaccine safety studies, with additional validation completed in previous studies. To further assess the potential for misclassification, more sensitive and specific algorithm versions can be applied in sensitivity analyses. Differential ascertainment of outcomes is a potential limitation within the comparative cohort design if the vaccinated and unvaccinated populations have different healthcare seeking behaviour which not only influences their probability of vaccination, but also access to care for outcomes. Given this study focuses on populations with chronically managed conditions, differential outcome reporting is not anticipated due to the frequent nature of healthcare encounters in the populations of interest; but differential healthcare seeking behaviour will still be adjusted for (as feasible) through PS-based ATT weighting.

Further, outcome onset is defined by the timing of the healthcare encounter at which the diagnosis is recorded. For outcomes with rapid onset that are serious enough to warrant an interaction with the healthcare system, the date of onset will closely reflect the date of the diagnosis associated healthcare encounter. Some outcomes may have a longer lag period between symptom onset and diagnosis. For these outcomes, sensitivity analyses can be used to explore potential impact of mis-specification of outcome onset.

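### Day 0 is the administration date, but SNDS holds no injection date and the protocol does not say which recorded date stands in for it, which matters for the short risk windows

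*Protocol*

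**What the plan says.** Protocol section 9.1: "The index date for the vaccinated individuals will be defined as the date of administration of ABRYSVO". The notes to Table 1 in section 9.3.2.1 carry this to every window: "Day 0 is the date of vaccine administration".

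The exposure definition in section 9.3.1 is wider: "Exposure will be based on recorded prescription, dispensing, or administration of ABRYSVO". It gives no rule for choosing among the three dates.

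For SNDS, section 9.3.1 states: "Exposure information is captured based on vaccines dispensed in community outpatient pharmacies", "with dates of prescription and dispensing". Section 9.4.5 adds: "Information on underlying medical indication or date of drug injection are not available".

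Three other places bear on this:

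- Section 9.4 asserts that every source can supply high-quality data on ABRYSVO products and dates.
- Section 9.9 refers back to 9.3.1 for vaccination dates and says of the SCRI that it "is not subject to potential misclassification of vaccination status".
- Section 9.7.3.3 pools the main estimates from each data source, so SNDS enters the pooled result for each outcome that it contributes to.

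**The concern.** The protocol fixes time zero at an event that one of its five sources cannot date. A dispensed dose may be injected the same day, some days later, or never. If it is injected later, the recorded risk window opens too early. Events that truly follow vaccination then fall after the window closes, and in the SCRI they can be counted in the post-vaccination control interval.

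The exposed primary windows are the short ones in Table 1: anaphylaxis (0-1), myocarditis and pericarditis (1-7), pericarditis (1-14), and the two outcomes combining thrombosis with thrombocytopenia (1-15). All are analysed by both cohort and SCRI. The error runs toward no effect, which is the unfavourable direction in a safety study. The limitations in section 9.9 cover unrecorded vaccinations and uncertain risk periods, but not a lag between recorded date and injection, nor doses dispensed and not given.

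**Working it through.** **1. The dates side by side.** Index date and day 0: administration (9.1, 9.3.2.1). Exposure: prescription, dispensing or administration (9.3.1). SNDS: prescription and dispensing dates, no injection date (9.3.1, 9.4.5). Read literally, day 0 cannot be set in SNDS, and no text names a substitute.

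**2. The plan's own sizes.** Table 2 follows n per cohort = (z₀.₉₇₅ + z₀.₈₀)² × (p + Rp) / (p(R − 1))², with (1.960 + 0.842)² ≈ 7.849. For anaphylaxis at 10 per 100,000 person-years the table uses p = 0.0000005.

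- R = 2: 7.849 × 3 / 0.0000005 ≈ 47.1 million (Table 2: 47,093,279).
- R = 10: 7.849 × 11 / (0.0000005 × 81) ≈ 2.13 million (Table 2: 2,131,795).

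All 24 rows of Table 2 reproduce. They take day 0 as known.

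**3. Share of doses injected after the window (cohort).** Let p_late be the share of recorded doses injected after the window closes. Assume those doses contribute background risk only and the others keep their full excess. Then observed IRR = 1 + (1 − p_late)(R − 1). The documents give no value, so 20% to 80% is assumed.

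- R = 10: 1 + 0.8 × 9 = 8.2; 1 + 0.2 × 9 = 2.8.
- R = 3: 1 + 0.8 × 2 = 2.6; 1 + 0.2 × 2 = 1.4.
- p_late = 0 (all injected on the recorded day): no change.

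By the Table 2 formula, detecting 2.8 instead of 10 takes 7.849 × 3.8 / (0.0000005 × 3.24) ≈ 18.4 million per cohort instead of 2.13 million. This describes a cohort misdated throughout at the 80% end, not the pooled study.

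**4. Constant lag.** Assume a lag of L days, a window of W days (L ≤ W) and excess risk spread evenly over the true window. For the SCRI, also assume a control interval of equal length directly after the risk interval, as in the protocol's 42-day GBS example.

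- Cohort: 1 + (R − 1)(W − L)/W.
- SCRI: [W + (R − 1)(W − L)] / [W + (R − 1)L].

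Worked case with R = 2, W = 7, L = 3: cohort 1 + 4/7 = 1.57; SCRI (7 + 4)/(7 + 3) = 1.10.

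| Window (days), true ratio 2 | Lag | Cohort | SCRI |
|---|---|---|---|
| Anaphylaxis 0-1 | 1 | 1.50 | 1.00 |
| Myocarditis and pericarditis 1-7 | 1 | 1.86 | 1.62 |
| Myocarditis and pericarditis 1-7 | 3 | 1.57 | 1.10 |
| Myocarditis and pericarditis 1-7 | 5 | 1.29 | 0.75 |
| Pericarditis 1-14 | 3 | 1.79 | 1.47 |
| Pericarditis 1-14 | 7 | 1.50 | 1.00 |
| Thrombosis with thrombocytopenia 1-15 | 3 | 1.80 | 1.50 |
| Thrombosis with thrombocytopenia 1-15 | 7 | 1.53 | 1.05 |
| GBS 1-42, for contrast | 7 | 1.83 | 1.57 |

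Under this model the cohort IRR stops at 1. Only the SCRI can fall below it.

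**5. Size of SNDS.** Stated populations in millions: SNDS 67, CPRD Aurum 16 active, SIDIAP 5.8, VID 5, EpiChron 1.3 active. SNDS is 67/95.1 = 70%. Counting 47 for CPRD and 2 for EpiChron (historic patients included), it is 67/126.8 = 53%. These are people of all ages covered, not people vaccinated.

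**The case against.** The best defence is that the protocol allows for imprecise timing. Section 9.9 concedes that uncertain risk periods can misclassify and attenuate in both designs. Section 9.7.4 lists extended windows for acute outcomes, alternative SCRI intervals and a washout between intervals. Section 9.7.3.3 plans a heterogeneity check and a forest plot by source, which could reveal a null SNDS estimate beside raised ones. Source-specific date rules could also sit in the SAP.

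This stands in part. The sensitivity analyses are optional, are not specific to SNDS and leave the main pooled estimate unchanged. A forest plot shows a discrepancy without saying that the date is its cause. The index date, the exposure rule and the claims about data quality are fixed in the protocol itself, and there they conflict.

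Several stronger readings are tempting but unsupported:

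- *SNDS will dominate the pooled estimate.* Pooling weight depends on events among eligible vaccinated adults. The documents give no ABRYSVO uptake by source, only population covered.
- *EpiChron has the same defect.* Section 9.3.1 describes its exposure "with prescriptions and dispensation of drugs in community pharmacies", but section 9.4.4 lists vaccination as a data stream of its own. Whether that stream holds administration dates is not stated.
- *The 0-3 day window is affected in the primary analysis.* It is a sensitivity window for atrial fibrillation and supraventricular arrhythmias. The primary arrhythmia window is 1-365 days.
- *Section 9.9 calls the SCRI free of all exposure misclassification.* It speaks of vaccination status, not timing. The statement fails for doses dispensed and never given; on the date it is silent rather than wrong.
- *SNDS must be excluded from short-window outcomes.* That trades dating accuracy against precision, and Table 2 already needs about 2.1 million per cohort for anaphylaxis at an IRR of 10. Re-dating to a nursing act or visit claim is unproven, because section 9.4.5 says these claims carry no indication.

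**Conclusion.** The contradiction holds on the protocol's own text: day 0 is administration, SNDS has no injection date, and no rule fills the gap. Where injection falls after the recorded date, short-window estimates from SNDS are biased toward the null, and the SCRI can fall below 1. Followed as written, those estimates enter the pooled main result.

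The size is not known. The range of 8.2 to 2.8 for a true cohort IRR of 10, and of 2.6 to 1.4 for an IRR of 3, rests on an assumed 20% to 80% of doses injected after the window. The lag table rests on a constant lag and evenly spread excess risk. A reader might infer that the SNDS windows are certainly misplaced. The documents do not show that, since they give no lag and same-day injection causes no bias. Confidence is high in the inconsistency and low in its magnitude. The protocol should be changed.

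**What to change.** 1. In section 9.3.1, state for each source which recorded date sets day 0: administration where recorded, otherwise dispensing, and not a prescription alone. Align sections 9.1 and 9.3.2.1 with this.
2. For cohort and SCRI outcomes with short windows, prespecify pooled estimates with and without the sources that lack an administration date. That means SNDS, and EpiChron only if its vaccination stream proves to lack one.
3. In section 9.4, qualify the claim of high-quality vaccine dates. In section 9.9, restrict the SCRI statement, since a dispensed dose need not have been given.
4. Add the dispensing-to-injection lag and dispensed-but-not-given doses to the limitations, with the expected direction of bias for each design.

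The cost is protocol wording, one more pooled run and a less precise estimate where SNDS is left out.

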9.5. Study Size

The study will be conducted in a source population of the participating population-based electronic healthcare data sources from the VAC4EU network.

Table 2 shows the sample size calculations for select outcomes (i.e, anaphylaxis, GBS, and arrhythmia) using the comparative cohort design, assuming a two-sided alpha level of 0.05, an equal number of individuals for the vaccinated and unvaccinated cohorts, and a power of 80% across a range of IRRs. Given a lack of published background incidence rates for outcomes among the specific populations of interest (i.e, adults aged 60 and older who are immunocompromised or renally impaired or hepatically impaired), published incidence rates from general populations aged 60 years and older in VAC4EU databases⁴² were used to estimate rates in the unvaccinated cohort. As an example, to detect an IRR of 2 for arrhythmia with a power of 80% and two-sided alpha level of 0.05, a sample size of 1,178 vaccinated individuals and 1,178 unvaccinated individuals is needed. This assumes a background rate of 2,000 arrythmia events per 100,000 person-years among the unvaccinated individuals.

Outcome	Background rate	Background rate	Incidence rate	Samp	le size
	per 100,000 person-years ^a	per person during risk interval ^b	ratio	Vaccinated cohort	Unvaccinated cohort
Anaphylaxis	10	0.0000005	2	47,093,279	47,093,279
			3	15,697,760	15,697,760
			5	5,886,660	5,886,660
			10	2,131,795	2,131,795
	15	0.0000008	2	29,433,300	29,433,300
			3	9,811,100	9,811,100
			5	3,679,163	3,679,163
			10	1,332,372	1,332,372
Guillain-	6	0.0000069	2	3,412,557	3,412,557
Barré syndrome			3	1,137,519	1,137,519
Synarollic			5	426,570	426,570
			10	154,478	154,478
	10	0.0000115	2	2,047,534	2,047,534
			3	682,512	682,512
			5	255,942	255,942
			10	92,687	92,687
Arrhythmia	2,000	0.0200000	2	1,178	1,178
			3	393	393

Table 2Number of Individuals Needed to Detect Different Rate Ratios for Selected
Outcomes with a Range of Background Rates

PFIZER CONFIDENTIAL CT24-WI-GL02-RF02 5.0 Non-Interventional Study Protocol Template For Secondary Data Collection Study 01-Aug-2023 Page 41 of 72

Table 2Number of Individuals Needed to Detect Different Rate Ratios for Selected
Outcomes with a Range of Background Rates

Outcome	Background rate	Background rate	Incidence rate	Samp	Sample size		
	per 100,000 person-years ^a	per person during risk interval ^b	ratio	Vaccinated cohort	Unvaccinated cohort		
			5	148	148		
			10	54	54		
	5,000	0.0500000	2	471	471		
			3	157	157		
			5	59	59		
			10	22	22		

Notes:

a. Due to a lack of published background incidence rates of outcomes of interest among the study-specific population (i.e., adults aged 60 and older who are immunocompromised or renally impaired or hepatically impaired), background rates of outcomes among adults aged 60 and older from general European populations ,published in Supplement 1, Table 1 of Willame et al (2023)⁵³ using VAC4EU databases were used as the basis of sample size and power calculations. A range of background rates were used to address potential differences in underlying rates between the general and study-specific populations (i.e., higher and lower background incidence rates of outcomes than were published in Willame et al.). Sample size and power calculations may be updated during the study as new and relevant background rate data emerges. Key study design features will be reviewed in the light of any updated sample size and power calculations.

b. Assuming a two-sided alpha = 0.05, power of 80%, and a ratio of 1:1 of vaccinated to unvaccinated. Examples of background IR accounting for the risk window:

Anaphylaxis (10/100,000 person-years)/365 * risk window (risk window 2 days) = 0.0000005

GBS (6/100,000 person-years)/365 * risk window (risk window 42 days) = 0.0000069

Arrhythmia (2,000/100,000 person-years)/365 * risk window (risk window 365 days) = 0.02

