The exposure of interest is ABRYSVO vaccination, which will be obtained from pharmacy dispensing records, general practice records, immunization registers, vaccination records, medical records, or other secondary data sources. Outcomes will be identified in participating databases with algorithms based on codes for diagnoses, procedures, and treatments. Standard algorithms for each outcome definition will be applied to participant data sources, based on the results of the ACCESS project, and will be tailored to the data source. Potential covariates may include the following information, as available in each data source: demographics; personal lifestyle characteristics; and clinical characteristics including comorbidities, comedication use, healthcare utilisation descriptors, other vaccinations, and surrogates of frailty. Covariates will be identified on the index date (or during the 12-month baseline period prior to the index date). These variables will be used to further characterize the patient populations of interest and/or to control for confounding.

Data sources

The study will utilise data from the following selected data sources: Clinical Practice Research Datalink (CPRD) Aurum (UK), Valencia Health System Integrated Database (VID) (ES), Sistema d'Informació per el Desenvolupament de la Investigació en Atenció Primària (SIDIAP) [Information System for the Improvement of Research in Primary Care] (ES), EpiChron Research Group on Chronic Diseases at the Aragon Health Sciences Institute (EpiChron) (ES), and Système National des Données de Santé (SNDS)[French nationwide healthcare database] (FR).

Study size

All individuals who meet the eligibility criteria during the study period in the select data sources will be included. The sample size will depend on the number of individuals administered ABRYSVO identified within the data sources during the study period, which will increase over time. The relative increases in rates to be detected will vary across outcomes of interest. For example, analyses using a comparative cohort design will have sufficient power (80%) to detect a 2-fold and 3-fold increased rate of arrhythmia associated with ABRYSVO, with a sample size of 1,178 and 393 individuals per cohort, respectively, assuming a baseline rate of 2,000 arrhythmia events per 100,000 person-years and equal numbers of individuals in the vaccinated and unvaccinated cohorts.

Data analysis

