- 3. Third, following conversion to harmonised study variable sets, R programs for the calculation of incidence will be distributed to data access providers for local deployment. The aggregated results produced by these scripts will then be uploaded to the DRE for pooled analysis and visualisation (see Figure 4). The DRE is made available through UMCU/VAC4EU (https://www.andrea-consortium.org/). The DRE is a cloud-based, globally available research environment where data are stored and organised securely and where researchers can collaborate (https://www.andrea-consortium.org/azure-dre/).

[figure not shown]

Figure 4 Data Management Plan

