9.7.3.3. Meta-analysis

For both the comparative cohort and SCRI designs, an appropriate random-effects metaanalytic method will be applied to the main estimates from each data source to obtain a combined effect estimate. The heterogeneity across data sources will be checked, and a forest plot will be produced with the data sources and the pooled estimate.

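### The 80% power in Section 9.5, Table 2 and the abstract holds for one pooled two-cohort comparison, not for the planned random-effects pooling of five per-source estimates, which has less power at the printed sizes

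*Protocol*

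**What the plan says.** Protocol Section 9.5 sizes the comparative cohort design "assuming a two-sided alpha level of 0.05, an equal number of individuals for the vaccinated and unvaccinated cohorts", with 80% power. For arrhythmia, "This assumes a background rate of 2,000 arrythmia events per 100,000 person-years among the unvaccinated individuals"; the Table 2 footnote converts this to a per-person risk: "Arrhythmia (2,000/100,000 person-years)/365 * risk window (risk window 365 days) = 0.02". The worked example is that "to detect an IRR of 2 for arrhythmia with a power of 80% and two-sided alpha level of 0.05, a sample size of 1,178" is needed in each cohort. The abstract says that the cohort analyses "will have sufficient power (80%) to detect a 2-fold and 3-fold increased rate of arrhythmia" with a "sample size of 1,178 and 393 individuals per cohort, respectively". Neither place mentions the number of data sources or variation between them.

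The analysis is distributed. Five sources are listed in Section 9.2. Under Section 9.6.2 the programs run locally and only aggregated results are sent on; Section 9.6 adds: "The aggregated results produced by these scripts will then be uploaded to the DRE for pooled analysis". Section 9.7.3.1 describes a weighted Poisson model for the cohort comparison, and Section 9.7.3.3 says that a random-effects "method will be applied to the main estimates from each data source to obtain a combined effect estimate". The abstract is softer here, saying only that such methods may be used. No estimator, source shares or between-source standard deviation are given.

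**The concern.** The power statement describes a comparison in which all individuals sit in one dataset. The planned combined estimate is made differently. Each source yields a log-IRR from its own few events, and the pooling step then estimates a between-source variance from five values. Two things follow even if the true IRR is the same everywhere. The estimated between-source variance is sometimes above zero by chance, which widens the interval. Inverse-variance weighting of sparse log-IRRs also pulls the pooled value towards 1.

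In a safety study the error is in the unfavourable direction: a real doubling or tripling would be missed more often than stated, and a null pooled IRR at these sizes would look more reassuring than it is. The figures may also be used. Section 9.2.4 lets uptake and exposure accrual decide whether vaccination seasons are added, and the Table 2 footnote says that key design features will be reviewed against updated size calculations.

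**Working it through.** **Reproducing the printed sizes.** Inputs from Section 9.5: two-sided alpha 0.05, power 80%, 1:1 cohorts, L0 = 0.02 per person over 365 days, L1 = IRR × L0.

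n per cohort = (1.960 + 0.842)² × (L0 + L1) / (L1 − L0)²

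- IRR 2: 7.849 × 0.06 / 0.02² = 1,177.3, rounded up to 1,178.
- IRR 3: 7.849 × 0.08 / 0.04² = 392.4, rounded up to 393.
- GBS at 0.0000069, IRR 2: 3,412,556.4, rounded up to 3,412,557.

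All three match Table 2. The formula has one stratum and no between-source term.

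**Events per source.** With 1,178 per cohort as a total split equally over five sources, each has 235.6 per cohort. That is 235.6 × 0.02 = 4.7 expected comparator events and 235.6 × 0.04 = 9.4 expected vaccinated events.

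**Large-sample power after pooling (equal split, IRR 2).** Let tau be the between-source SD of the log-IRR; the protocol gives none, so 0 to 0.3 is assumed.

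var = 1/(n·L0) + 1/(n·L1) + tau²/5, and power = Φ(ln 2 / √var − 1.96)

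- tau 0: var = 1/23.56 + 1/47.12 = 0.0637; power 78.4%.
- tau 0.2: var = 0.0637 + 0.008 = 0.0717; power 73.5%.
- tau 0.3: var = 0.0637 + 0.018 = 0.0817; power 67.9%.

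This treats tau and the within-source variances as known, so it is optimistic for such small counts.

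**Simulation.** Poisson counts per source and cohort; log-IRR with variance 1/y1 + 1/y0; 0.5 added in a source with one zero cell; sources with no events dropped; no propensity weighting or censoring; 40,000 to 100,000 runs per scenario. Three assumed splits: equal; in proportion to the database populations in Section 9.4 (16 : 5 : 5.8 : 1.3 : 67 million, all ages); and 90% of individuals in one source.

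Power for IRR 2, n = 1,178 per cohort, tau = 0:

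| Analysis | Equal | By database size | 90% in one source |
|---|---|---|---|
| Single pooled comparison | 80-81% | 80-81% | 80-81% |
| DerSimonian-Laird | 67% | 67% | 71% |
| REML | 68% | 68% | 69% |
| Paule-Mandel | 67% | 67% | 71% |
| Maximum likelihood | 70% | 74% | 78% |
| Hartung-Knapp interval | 49% | 55-56% | 62% |

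- Fixed-effect inverse-variance pooling, which is not the planned method, gives 73-79% on the same data.
- DerSimonian-Laird at tau 0.2: 63-66%. At tau 0.3: 59-64%.
- Hartung-Knapp at tau 0.3 falls to about 44% with an equal split. A more conservative modified version gives about 31% even at tau 0.
- IRR 3, n = 393, tau 0: single pooled comparison 81%; DerSimonian-Laird 61% (equal), 66% (by database size), 67-68% (90% in one source). The median pooled IRR is 2.6-2.7 against a true 3, which shows the pull towards 1.

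**Size for 80% under one set of assumptions.** DerSimonian-Laird, tau 0, no weighting, IRR 2: about 1,510 per cohort with an equal split (1,510/1,178 = 1.28) and about 1,660 with the split by database size (1,660/1,178 = 1.41).

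**The case against.** The strongest reply is that Table 2 contains no mistake: it states its assumptions, and under them 1,178 is right. That stands. A reader might infer an arithmetic error in Table 2, and the documents do not support that; the fault is that the 80% is stated without the condition under which it holds.

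Second, the choice of estimator belongs to the SAP. That also stands, and it rules out another inference, that power is about 67% at best. The 67% needs DerSimonian-Laird, no heterogeneity and the equal or database-size split. Other admissible choices give up to about 78%, and others well below 67%. But the power claim and the random-effects step are both already in the protocol, and no two-stage method tried reached 80% at the printed sizes.

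Third, Section 9.5 does not say that the sizes are totals to be divided over sources. If every source alone reached 1,178 per cohort (5 × 1,178 = 5,890 in all), the claim would hold within each source. The text does not say this either, and Section 9.5 speaks of the source population of the participating databases together. If 1,178 is the total and nothing is pooled, as the abstract's wording would allow, one fifth of it gives only about 18-19% power in a single source.

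Fourth, little hangs on the numbers, because the abstract says that all eligible individuals are included. This limits the weight of the point. A reader might infer that the study is underpowered; the documents do not support that, since the sizes are not targets and the eventual numbers are unknown. The Table 2 footnote does allow recalculation, but for new background rates, not for the analysis model.

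**Conclusion.** The point holds as a mismatch between the stated power and the planned analysis. The sizes 1,178 and 393 are correct for one pooled two-cohort comparison. Read as totals over five sources, they give less than 80% under the random-effects pooling of Section 9.7.3.3.

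The direction is firm. The amount is conditional: roughly 49-78% for IRR 2 across the tabulated estimators and splits with no heterogeneity, and lower for any one estimator once the true IRR varies between sources. These figures ignore propensity weighting and censoring, and the splits are assumptions; all-age database populations are only a rough stand-in for vaccinated, impaired adults aged 60 and over. The correction is worth making because it is cheap and the present wording overstates sensitivity to harm. It does not call the design into question.

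**What to change.** In Section 9.5, Table 2 and the abstract:

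1. State that each printed size is a total over all data sources for one population, and that it gives 80% power only for a single pooled comparison with no between-source variance.
2. Report the power of the printed sizes, or recomputed sizes, under the two-stage random-effects pooling as a range over named estimators, assumed source shares and a between-source SD range (for example 0 to 0.3).
3. Label any replacement size with its conditions. About 1,510-1,660 per cohort for IRR 2, for instance, depends on DerSimonian-Laird, zero heterogeneity, no propensity weighting and the assumed shares, and should not be printed as a general requirement.
4. Make the abstract and Section 9.7.3.3 agree on whether the meta-analysis will or may be done.

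The cost is a short simulation and a text edit. The power statement becomes less favourable. Enrolment, data collection and the analysis itself do not change, and the choice of estimator can stay with the SAP.
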